### 3) *Home-based CR + mHealth (HOM+):*

Participants will be provided paper copies of educational content at the time of event/discharge.

These participants will be provided access to the mHealth platform (as noted above). The mHealth platform provides “e-Learning modules” with factsheets, videos, quizzes, and questionnaires (coinciding with activities being conducted during the CON program), a Social Network Module will allow patients to communicate via secure network with other patients who are part of their invited network. The Social Network Module also allows for secure two-way interaction with healthcare providers if patients are experiencing signs or symptoms suggestive of worsening condition.

Participants will be given a blood pressure cuff and scale with which they are asked to measure their blood pressure and weight. The device setup will be performed onsite or at home (via video visit after shipping devices to the participant’s address). This data will be uploaded to the mHealth Personal Health Record Module. This module allows patients to upload, archive, and retrieve personal health data (e.g. fitness tracker data, heart rate monitor data, blood pressure recordings, etc.) and record vital signs, symptoms, treatments, and medical history.

Participants in this HOM+ group will be encouraged to exercise three days per week while also completing the additional questionnaires and educational content provided by the mHealth platform in accordance with the CR program. Participation will be tracked using web/internet analytics. Subjects in this arm of the study will have a remote visit (either video or telephone visit) with Cardiac Rehab staff once a week for 12 weeks.

Due to recent CMS changes, Home-based CR for patients randomized to the HOM+ group will be paid for by the study.

This three arm trial will allow us to make comparisons between a hybrid program of center-based CR which incorporates mHealth remote case management technology (CON+) to a traditional center-based program

alone (CON) as well as comparisons between home-based mHealth remote case management alone (HOM+) to a traditional center-based program (CON).

### **3.4 Participant Recruitment**

*[[Male and Female patients, aged 18-80 years, who are identified as eligible for conventional CR will be recruited from the Mayo Clinic Health System (MCHS) (or our subcontract site University of Minnesota Medical Center [M Physicians/Fairview Health System]) by clinical research coordinators, referring physicians, and/or CR staff. We will make every attempt to recruit equal numbers of both men and women and appropriate distribution of minority participants.]]*

Inclusion Criteria: Patients must own, or have reliable access to, a smartphone or desktop computer with internet access, and an e-mail address. Eligible patients will have a history of one of the following: acute myocardial infarction/acute coronary syndrome, stable angina pectoris, percutaneous coronary intervention, or heart failure. Additionally, patients who underwent a surgical procedure which includes an indication for cardiac rehabilitation (coronary artery bypass surgery, heart valve repair/replacement, or heart transplant) will be enrolled but will only complete 6-minute walk test for measurement of exercise capacity per clinical practice guidelines.

Exclusion Criteria: Patients referred to CR with ventricular assist devices are not eligible. Patients who do not own, or have access to, a smartphone or desktop computer with internet access will not be recruited. Patient unable/unwilling to provide informed consent will not be enrolled.

The annual population of eligible CR patients at Mayo Clinic varies by diagnosis. As highlighted by Ades and colleagues report an annual nation-wide incidence of ~1,963,000 myocardial infarction, percutaneous coronary intervention, and systolic heart failure patients eligible for CR compared to only 395,000 coronary artery bypass surgery patients. While this list is clearly not inclusive of all eligible referral diagnoses, it provides an illustration of the disproportionate number of surgical vs. non-surgical patients eligible for CR. Importantly, despite the significantly larger number of non-surgical patients eligible for CR, it has been reported that CABG patients demonstrate higher rates of participation in CR^43.

*[[Mayo Clinic has developed an in-house referral protocol for all patients meeting CR eligibility guidelines. Specifically, all patients visiting the clinic and/or hospital for one of the above inclusion criteria can be identified by our research team through the medical records, screened for eligibility, and approached to determine interest/willingness to participate in the study. This approach will maximize our potential to identify eligible individuals for screening and all patients who meet all eligibility criteria will be asked to participate. In 2018, the Rochester, MN CR program provided services for 459 new patients. Of those patients 68 were self-identified minority race or ethnicity (~15%) and 157 were women (~34%). Moreover, 365 patients were referred for non-surgical indications (~80%) which would meet the inclusion criteria of this proposal. Additionally, we have enlisted the assistance of an additional site in the Minneapolis/St. Paul metropolitan area (Hennepin County). The University of Minnesota Medical Center (M Physicians/Fairview) health network has 10 cardiac rehabilitation locations which provide cardiac rehabilitation services to ~4,000 new patients annually. Of these patients, ~3,000 receive their services within the Minneapolis/St. Paul urban area, many of which are from diverse racial and ethnic backgrounds.]]* We will maximize our retention by providing participants with remuneration for their time in the research program. This will include \$50 for the baseline visit, \$50 for the first follow-up visit at the end of the intervention, and \$50 for the final follow-up visit at 1-year post event. Payments will be made at the time the participant completes the final follow-up visit or informs a study team member of their desire to withdraw from the study.

### **3.5 Methodology – Specific Programmatic and Functional Methods and Measurements**

All metrics will be collected at baseline (within 2 weeks of beginning study arm activities) prior to participation in any arm of the research program, at approximately three-months (+/- 2 weeks) post enrollment which will coincide with 36 sessions of CR (three sessions per week for 12 weeks) for those enrolled in the CON or CON+ study arms, as well as at 1-year (+/- 4 weeks) post event.

Demographics, Anthropometrics, and Medical History: Standard demographics and anthropometrics will include age, height, weight, body mass index, waist circumference, hip circumference, and resting blood

pressure. Medical history will include current diagnoses, current medications, family disease history, and smoking history.

**Body Composition:** Body composition will be measured by the following standard metrics: 1) body mass index (BMI), 2) waist to hip ratio, 3) dual-energy X-ray Absorptiometry (DXA). We will measure DXA in all participants at baseline and at the first follow-up visit if available. Measurement of DXA will allow for compartmentalization of total body mass into total body lean and fat mass as well as regional distribution of these quantities. This additional detail may be useful in sub/exploratory analysis examining the impact of home-based electronic CR programming on regional fat and muscle distribution. Importantly, all participants will have height and weight measured clinically which will allow for the universally accepted assessment of BMI (weight in kilograms divided by the height in meters squared) as well as waist to hip ratio. This data can be collected at the time of enrollment in the research program and during each of the two follow-up study visits.

**Blood Chemistries:** All fasting blood chemistry measures will be conducted by standard clinical protocols in the Mayo Clinic laboratories. Measures will include a basic lipid panel (total cholesterol, high density lipoprotein cholesterol, low density lipoprotein cholesterol, and triglycerides), blood glucose, hemoglobin, and hemoglobin A1c. These measures will be conducted at the time of enrollment in the research program and during each of the two follow-up study visits.

**Physical Activity:** Self-reported physical activity levels will be assessed using the International Physical Activity Questionnaire (IPAQ) and the Duke Activity Status Index (DASI). These activity questionnaire quantify participant's activity patterns in categories of vigorous, moderate, and leisure. This will be measured during the week immediately prior to beginning study arm activities and during each of the two follow-up study visits.

**Exercise Capacity:** Exercise capacity will be measured by the following standard metrics: 1) six-minute walk test (6MWT), 2) a standard 12-lead ECG monitored symptom-limited exercise stress test or cardiopulmonary exercise test to include measurement of oxygen consumption (CPET). The CPET will be the preferred measure of exercise capacity as measurement of peak oxygen consumption ( $\text{VO}_{2\text{peak}}$ ) is considered the Gold standard measure of fitness. For standardization, the 6MWT will provide absolute distance walked and percent of age predicted distance walked as a universally accepted assessment of exercise capacity. The CPET will be conducted in the Mayo Clinic Integrated Stress Center as standard clinical protocol. These measures of exercise capacity will be conducted at the time of enrollment in the research program and during each of the two follow-up study visits.

**Dietary Patterns:** Dietary pattern will be obtained using a standard food frequency questionnaire at the time of enrollment and during each of the two follow-up study visits.

**Quality of Life:** Physical and mental health-related quality of life will be assessed using the validated 9-item Patient Health Questionnaire (PHQ-9) and the validated Dartmouth 9-item Short-Form health survey at the time of enrollment and each of the two follow-up study visits.

**mHealth Remote CR Case Management Platform:** *The mHealth remote case management platform developed specifically for CR is an asynchronous platform consisting of several services intended to empower patients by raising their awareness about their health condition. These services give patients the opportunity to better understand, manage, and control their health condition for an improved quality of life.*

*One of the main services is the learning module which provides patients the opportunity to learn about their health condition to better manage their disease by understanding how to adapt their lifestyle. This module offers a number of relevant resources that can be combined to form learning sessions organized in levels. Only the completion of a level will unlock access to the next level allowing CR staff (and research staff) the ability to track completion of specific educational content. The content will be defined and customized in line with the conventional CR programming. The different types of e-learning resources include factsheets, videos, quizzes, and questionnaires. Content modules (including didactic information and time for completion of exercise) are designed to be completed within a 45-60 minute timeframe, similar to conventional center-based programming.*

*This platform also includes a personal health record module which allows patients to manage their health data. Each patient can upload and archive information concerning their health. The health record section includes the ability for patients to enter general information about their health, symptoms, treatment, medical history, as well as provides a dashboard where their health data is then represented in table and graphic format. The data*

The social network module provides patients the ability to communicate, within a secure network, with their healthcare professionals (CR staff or research staff) who are part of their network. The network only includes patients and healthcare professionals involved in the CR program as part of the platform. Patients and care givers can have direct interactions through a chat function. Patient-caregiver (CR staff or research staff) interactions will only occur during regular outpatient clinical hours. This allows patients to ask questions, provide feedback, and communicate any possible issues that may arise. This also allows the CR staff and/or research staff to provide feedback, answer questions, provide clarification, and make changes to the individualized treatment plan (as would occur during conventional center-based CR during face-to-face conversations and interactions). Should an event or symptoms arise, patients will be instructed to go to their local emergency room and/or call 911 for assistance. The process for seeking medical attention is the same for all patients outside the center-based CR facility. Patients are automatically in contact with the care team involved in their care (medical directors, case managers, dietitians, exercise physiologists, etc.).

*The platform home page has been designed to enhance the user experience. Any resource from any module can be pushed directly to the homepage by the staff to avoid excessive navigation within the platform. It can be used to view information messages, to access specific tasks, and to setup reminders to perform certain tasks. The home page is scalable in time. It also evolves with patient progress within his/her program. The goal is to provide personalized care by displaying the right information at the right time to the right patient.*

*All modules (e.g., services) are independent from each other and can be activated or deactivated on request. All encompass sub-modules allowing for individualized patient progress through the program. The content of the sub-modules is fully customizable so it can be easily and effectively modified based on patient needs (e.g., removing diabetes information for non-diabetics or including smoking cessation information for current smokers, etc.) and remain in-line with center-based CR program content offerings.*

**Website Analytics:** We will track and record all web-analytics associated with the usage of the mHealth remote CR case management platform for the purpose of this study. Website usage including time to first usage (onboarding to sustained login), number of times a patient visits their individual portal (per day/week/month), the amount of time a patient spends in their portal per visit, the number of times a patient views specific educational content, completion of educational content, time to completion of educational content modules, amount of time spent viewing and displaying educational content, and quantity of vital statistics recorded will be measured. This data will allow for the determination of HOM+ and CON+ patient groups CR component uptake and utilization and thus will be used as a composite marker for participation and adherence to the CR program components for comparison to the CON group.]]

*All patients, regardless of which arm they are in, will be offered the option to participate in a substudy where they are asked to wear a Fitbit to track their physical activity while participating in the main study.*

### Table 4. Timeline, Milestones, and Deliverables

[illegible]

(Deliverable)												
Biannual stakeholder meetings (Milestones)	X		X		X	X	X	X	X	X	X	X
Obtain Institutional Review Board approval (Deliverable)		X										
RAVE database creation		X										
ClinicalTrials.gov registration		X										
Participant enrollment and Intervention			X	X	X	X	X	X	X	X	X*	
Participant enrollment (n=50 in Y1 ~ 15%) (Milestone)			X									
Participant enrollment (n=95 in Y2 ~ 29%) (Milestone)				X	X							
Participant enrollment (n=94 in Y3 ~ 28%) (Milestone)						X	X					
Interim data analysis (Deliverable/Milestone)								X				
Participant enrollment (n=94 in Y4 ~ 28%) (Milestone)								X	X			
Participant enrollment (n=0 in Y5 ~ 0%) (Milestone) (Follow-up Only)										X		
Final data analysis (Deliverable/Milestone)											X	X
Presentation/Manuscript preparation (Deliverable)											X	X

\* Follow-up only

### [[3.7 General Statistical Considerations

Our detailed statistical approaches and power calculations are provided our Statistical Design and Power section of this application.

**Data Collection and Management:** Study data will be recorded in Medidata RAVE electronic data capture and case report forms. Edit checks, electronic queries, and audit trails are built into the system to ensure accurate and complete data collection and security. Case report forms are automatically rolled out according to the visit schedule to improve staff workflow and data quality. Data are exported nightly to Mayo Clinic's secure servers. Data will be deidentified wherever possible and access is managed under a controlled and monitored access request system. Patients will be randomized using a dynamic minimization algorithm available in Medidata Balance software to minimize imbalances between groups and ensure that the distribution of both women and minorities are appropriately distributed across all cohort arms of the study. Readmission and mortality endpoints will be collected by study personnel at follow-up visits and through electronic health records.

Briefly, **Specific Aim 1** will focus on Adherence and completion related to each arm. CON and CON+ arms will be compared to determine if addition of a mHealth platform results in increased attendance of CR sessions. Number of sessions will be compared between arms using a Wilcoxon rank-sum test. Completion frequency will be compared by Pearson chi-square test. Among CON+ and HOM+ arms, the primary adherence measure is number of total portal visits (with task completion), compared by Wilcoxon rank-sum test. **Specific Aim 2** will focus on changes in modifiable risk factors across the three arms. The primary outcome is functional capacity (VO2peak) at 3 months. Among the three treatment arms, there are two pairwise treatment hypotheses: (A) superiority of CON+ vs CON tested with two-sided alpha=0.025 and (B) non-inferiority of HOM+ vs CON tested with one-sided alpha=0.0125. This approach preserves an overall two sided alpha level 0.05 as described in the following Power and Sample Size section. Analysis of Covariance (ANCOVA) models will evaluate the relationship between the specified pairwise comparison arms and three month VO2peak, adjusted for baseline VO2peak. In analysis of Part A, we hypothesize superior efficacy of CON+ compared to CON. In the analysis of Part B, we first evaluate the lower bound of two-sided 0.025 confidence interval for the treatment effect difference between HOM+ and CON and compare to our pre-specified non-inferiority boundary of 2.8 mL/[min\*kg] (10% relative reduction vs assumed mean of 28 mL/[min\*kg] among CON patients, as specified in detail in the following Power and Sample Size section). If non-inferiority is demonstrated, we will subsequently perform a test of superiority of HOM+ compared to CON with two-sided alpha level 0.025. Secondary outcomes include measures of body composition, blood chemistries, 6MWT, and self-reported

physical activity, dietary patterns, and quality of life, as described. For those secondary outcomes where a pre-randomization observation is available, ANCOVA will be used to reduce residual variation and compare across all three study arms. Otherwise, ANOVA methods will be used when pre-randomization data are not available. Secondary outcomes will be assessed only with respect to superiority comparisons. Regression assumptions, including normality of residual distributions and homoscedasticity will be assessed by visual assessments of residual plots. Transformations will be applied when appropriate and non-parametric tests including Kruskal-Wallis tests will be considered when appropriate. Assessments at 1 year will be compared similarly as exploratory endpoints to determine if improvements at 3 months are sustained after completion of therapy. **Specific Aim 3** will focus on specific patient centered outcomes through one year post-randomization. The primary outcome is hospital readmission, compared across groups using a log-rank test. Cox proportional hazards models will estimate hazard ratios for pairwise group comparisons, with patients censored at loss to follow up or 1 year, whichever comes first. The endpoint of readmission alone will be described similarly, with cause-specific hazard ratios estimated by censoring at mortality in a Cox proportional hazards model. Mortality alone will be described using Kaplan-Meier estimates and a log-rank test, though we expect the mortality event rate to be low and any comparisons under-powered.

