### 3.3 Study Design

To address our specific aims we will use a single-center, prospective, three-arm, parallel group, randomized controlled trial design (**Figure 4**). At the time of identification of eligibility for participation (See below: Patient Population), patients will be randomized to one of three arms (1:1:1 ratio): **Arm 1** consists of patients randomized to conventional CR only (CON), **Arm 2** consists of patients randomized to conventional CR with the addition of the mHealth platform (CON+), and **Arm 3** consists of patients randomized to remote case management using the mHealth platform only (HOM+). Clinical metrics will include traditional cardiovascular risk factors with additional tracking of service utilization and adherence, and quality

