**Figure 4. Study Design Outline**

of life. Measures will be made at baseline (pre-intervention) and ~3-months (coinciding with completion of conventional CR). Additional follow-up will occur at 12 months post CR entry. Randomization to study arms will be done with a multidimensional dynamic allocation algorithm, minimizing imbalances in age, sex, body mass index, and race across study arms.

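### The primary VO2peak ANCOVA leaves out the four factors used in the minimisation, so its standard errors are somewhat too large and both primary tests are conservative

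*Combined protocol and SAP*

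**What the plan says.** Section 3.3 randomises 1:1:1 to CON, CON+ and HOM+ with a "multidimensional dynamic allocation algorithm, minimizing imbalances in age, sex, body mass index, and race across study arms". Section 3.7 confirms the method: "Patients will be randomized using a dynamic minimization algorithm available in Medidata Balance software".

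For Specific Aim 2, section 3.7 states: "The primary outcome is functional capacity (VO 2 peak) at 3 months". There are two primary comparisons: superiority of CON+ over CON at two-sided 0.025, and non-inferiority of HOM+ to CON at one-sided 0.0125 with a margin of 2.8 mL/min/kg. Both use an ANCOVA of the "specified pairwise comparison arms and three month VO 2 peak, adjusted for baseline VO 2 peak". None of the minimisation factors is named in that model. Secondary outcomes with a pre-randomisation value also use ANCOVA, with the stated purpose of reducing residual variation.

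On sites, section 3.3 describes a "single-center, prospective, three-arm, parallel group, randomized controlled trial design", while section 3.4 also recruits from "our subcontract site University of Minnesota Medical Center". Section 3.8 says that this site helps with recruitment as needed. Site is neither a listed minimisation factor nor a model term.

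Section 3.7 presents itself as a brief account and refers to a separate Statistical Design and Power section, which is not in the supplied text.

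**The concern.** Minimisation forces the arms to be alike on the chosen factors, so the treatment difference varies less from trial to trial than it would under simple randomisation. A model that omits those factors leaves their variance in the residual and computes its standard error as if they had been free to fall out of balance. The reported standard error then overstates the real uncertainty.

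At stake is efficiency in both primary comparisons. A true benefit of CON+ is a little harder to show, and so is true non-inferiority of HOM+, because the lower confidence bound sits further from the estimate than it should. The plan would pay the administrative cost of balancing on four factors without taking the full return in the analysis.

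**Working it through.** **Inputs from the documents.** One-sided alpha 0.0125 per comparison (equivalently two-sided 0.025), so z = 2.241. Four minimisation factors and one model covariate. The yearly enrolment milestones sum to 50 + 95 + 94 + 94 = 333, or 111 per arm.

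**Figures that can be reproduced.** 0.025 + 0.025 = 0.05, the stated overall alpha. 10% of 28 = 2.8, the stated margin. The sample size cannot be reproduced, because the supplied text gives no standard deviation, power or dropout.

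**Assumptions.** r is the share of residual variance, after baseline VO2peak, that the four factors explain. The documents do not give it, so it is shown as a range. Nominal power of 80% (z = 0.842) is also assumed, and balance on the factors is taken as nearly complete.

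**Formulas.** Scale the standard error reported by the baseline-only model to 1. The true standard error under minimisation is then about sqrt(1 − r).

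- Excess in the reported standard error: 1/sqrt(1 − r) − 1
- Actual one-sided size: 1 − Φ(2.241/sqrt(1 − r))
- Power, baseline-only model: Φ(0.842/sqrt(1 − r))
- Power, factors added: Φ((2.241 + 0.842)/sqrt(1 − r) − 2.241)

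| r | Standard error too large by | Actual size (nominal 0.0125) | Power, baseline only | Power, factors added | Gain (points) |
|---|---|---|---|---|---|
| 0 | 0% | 0.0125 | 80.0% | 80.0% | 0 |
| 0.02 | 1.0% | 0.0118 | 80.2% | 80.9% | 0.6 |
| 0.05 | 2.6% | 0.0107 | 80.6% | 82.2% | 1.6 |
| 0.10 | 5.4% | 0.0091 | 81.3% | 84.3% | 3.1 |

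Worked line for r = 0.10: sqrt(0.90) = 0.949. Baseline only: Φ(0.842/0.949) = Φ(0.887) = 81.3%. Factors added: Φ(3.083/0.949 − 2.241) = Φ(1.008) = 84.3%.

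**Simulation check.** Pocock-Simon minimisation with 333 patients, three arms, four binary factors, probability 0.8 of following the best-balancing arm, and 2,500 runs. The table shows HOM+ versus CON with no true difference, tested at two-sided 0.025.

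| r | Baseline only: true / reported SE | Rejection | Factors added: true / reported SE | Rejection |
|---|---|---|---|---|
| 0 | 0.0799 / 0.0806 | 0.022 | 0.0800 / 0.0806 | 0.023 |
| 0.05 | 0.0779 / 0.0806 | 0.019 | 0.0780 / 0.0786 | 0.023 |
| 0.10 | 0.0758 / 0.0806 | 0.018 | 0.0759 / 0.0765 | 0.023 |

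The simulation error on a rejection rate is about sqrt(0.025 × 0.975/2500) = 0.003. With the factors in the model, rejection agrees with 0.025 within that error and the reported standard error tracks the true one. Without them the reported standard error stays at 0.0806 while the true one falls. The true variability of the estimate is almost the same in both models (0.0758 and 0.0759 at r = 0.10), so what changes is the reported uncertainty.

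**The case against.** The strongest reply is that baseline-adjusted ANCOVA is a standard and valid primary analysis, that the error is in the safe direction, and that it may be negligible. That age, sex and body mass index relate to VO2peak does not settle the matter. What counts is what they add once baseline VO2peak is in the model, and baseline VO2peak should already carry much of that information. At r = 0.02 the effect is too small to matter. The missing statistics section may also list these covariates. All of this stands. It limits the size of the point without removing it, because the model as stated still omits the factors on which the trial allocates.

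A reader might infer more, in four ways.

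- **That the tests are invalid.** They are not. Error rates fall below nominal, including for the non-inferiority claim.
- **That power rises from 80% to the adjusted figure.** This double-counts. If minimisation has already reduced the true variance, the unadjusted test also has slightly more than 80% power, so the gain is the difference between the two power columns.
- **That patients without a 3-month test are dropped, tilting the result towards HOM+.** No passage says so. The supplied text states no handling of missing 3-month VO2peak. Any figure for a shift would need assumed missingness rates by arm and an assumed deficit in the missing patients, and it would have to allow for the baseline adjustment. The direction is open too: CON asks for 36 center sessions, whereas HOM+ has weekly remote contact.
- **That the second site causes the same standard-error problem.** Site is not a listed minimisation factor, so omitting it does not create this mismatch, and the site's share of enrolment is unknown.

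**Conclusion.** The point holds as a modest, one-directional loss of efficiency. If the four factors explain 2% to 10% of the variance left after baseline VO2peak, the reported standard error is about 1% to 5.4% too large, the one-sided 0.0125 test runs at about 0.0118 to 0.0091, and adjustment is worth about 0.6 to 3 points of power from a nominal 80%. If baseline VO2peak already carries the information, the gain is close to zero. These figures rest on the assumed r, the assumed 80% power and near-complete balance on the factors. None of these can be checked against the supplied text.

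Separately, the single-center label in section 3.3 and the second recruiting site in sections 3.4 and 3.8 contradict each other and need to be reconciled.

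**What to change.** - In section 3.7, Specific Aim 2, add age, sex, body mass index and race to baseline VO2peak as prespecified covariates in the primary ANCOVA, with age and body mass index entered as continuous variables. Do the same in the secondary ANCOVAs.
- Bring the separate Statistical Design and Power section into line with this wording. If it already lists these covariates, only section 3.7 needs to change.
- Reconcile the single-center description in section 3.3 with the second site, and state that site enters the models as a covariate if that site enrols.

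The cost is a few sentences and a slightly longer model statement, settled before the final analysis. The four factors must already be known at randomisation to run the minimisation, so no new data are needed. The point does not require a different type of primary model, a change to the minimisation during the trial, or covariates in the Aim 3 Cox models. That last step would change the hazard ratio being estimated and is a separate decision.

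### The Aim 3 readmission analysis names no adjustment for qualifying indication, a recorded baseline factor; adding it would be a modest precision gain, not the correction of a bias

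*Combined protocol and SAP*

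**What the plan says.** **Analysis.** Section 3.7 says that Aim 3 "will focus on specific patient centered outcomes through one year post-randomization". The test is given as: "The primary outcome is hospital readmission, compared across groups using a log-rank test". The effect estimates are given as: "Cox proportional hazards models will estimate hazard ratios for pairwise group comparisons, with patients censored at loss to follow up or 1 year, whichever comes" sooner. Neither sentence names a stratum or a baseline covariate.

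**Allocation.** Section 3.3 (text with Figure 4) describes dynamic allocation in a 1:1:1 ratio, "minimizing imbalances in age, sex, body mass index, and race across study arms". Section 3.7 says the algorithm is to "minimize imbalances between groups and ensure that the distribution of both women and minorities are appropriately distributed across all cohort arms of the study". Indication is in neither list.

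**Indication.** Section 3.4 admits patients with a history of "acute myocardial infarction/acute coronary syndrome, stable angina pectoris, percutaneous coronary intervention, or heart failure", and adds bypass, valve and heart transplant surgery. Section 3.8 instead describes the trial as confined to non-surgical patients. Section 3.5 records diagnoses at baseline: "Medical history will include current diagnoses".

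**Contrast within the plan.** Section 3.7 adjusts the Aim 2 primary outcome for baseline VO2peak, and uses ANCOVA on secondary outcomes to cut residual variation. Aim 3 has no counterpart.

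Section 3.7 refers to a separate Statistical Design and Power section for detail. That section is not in the text reviewed, so the point is limited to what section 3.7 itself states.

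**The concern.** The eligible conditions run from stable angina to heart failure and, if section 3.4 governs, to surgery and transplant. It is reasonable to expect one-year readmission risk to differ between them, though the documents give no rates. If it does, an analysis that ignores indication has three consequences:

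- Some power is lost, because known variation in risk is left unexplained.
- The observed hazard ratio in the one trial that is run moves with any chance imbalance in the high-risk indications.
- The marginal hazard ratio lies slightly nearer to 1 than the hazard ratio within indication.

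Readmission is the primary outcome of an aim, and the information needed is already collected. If an imbalance shows up later, an adjustment added at that stage would look data-driven; one stated now would not.

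**Working it through.** The documents state no Aim 3 event rate, hazard ratio, alpha or power, so there is no figure of the plan's own to reproduce.

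**Inputs from the documents.** The Table 4 enrolment milestones are 50 + 95 + 94 + 94 = 333. The shares of 15.0, 28.5, 28.2 and 28.2% agree with the printed 15, 29, 28 and 28%. At 1:1:1 this is 333/3 = 111 per arm. Follow-up is one year.

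**Assumed inputs.** High-risk share p = 20-30%; prognostic hazard ratio h (high versus low risk) = 1.5-3; control one-year readmission r = 20-40%; two-sided alpha 0.05 per pair; no dropout; indication allocated at random between arms.

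**1. Chance imbalance between two arms.** SD of the difference in share = sqrt(2p(1-p)/111).
- p = 0.20: sqrt(0.32/111) = 0.054, so P(gap of at least 10 points) = 6.3%.
- p = 0.30: sqrt(0.42/111) = 0.062, so P = 10.4%.

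**2. Effect of a gap d on the unadjusted hazard ratio, with no treatment effect.** Ratio of mean hazards = [1 + (h-1)(p + d/2)] / [1 + (h-1)(p - d/2)], with d = 0.10:

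| h | p = 0.20 | p = 0.30 |
|---|---|---|
| 1.5 | 1.125/1.075 = 1.047 | 1.175/1.125 = 1.044 |
| 2 | 1.25/1.15 = 1.087 | 1.35/1.25 = 1.080 |
| 3 | 1.50/1.30 = 1.154 | 1.70/1.50 = 1.133 |

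On the log scale this is ln 1.044 = 0.04 to ln 1.154 = 0.14.

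**3. Sampling error for comparison.** Events per pair = 111r + 111[1 - (1-r)^HR]. This gives 33.9 at r = 0.2, HR 0.5, and 77.8 at r = 0.4, HR 0.7. The standard error of the log hazard ratio is about 2/sqrt(events) = 0.34 to 0.23, so the shift in step 2 is smaller than one standard error. Schoenfeld power at HR 0.6, unstratified, is 34, 47 and 59% for r = 20, 30 and 40%.

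**4. Power, unstratified to stratified (%).** Simulation with 6,000 replicates per cell, exponential times, censoring at one year, 111 versus 111. Monte Carlo error is about 0.6 points per figure; paired differences are more precise.

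| r, treatment HR | h 1.5, p 20% | h 2, p 20% | h 2, p 30% | h 3, p 20% | h 3, p 30% |
|---|---|---|---|---|---|
| 30%, 0.50 | 67.4 to 67.8 | 68.0 to 68.3 | 66.2 to 67.7 | 65.0 to 68.0 | 66.1 to 69.7 |
| 30%, 0.55 | 57.4 to 57.8 | 56.0 to 56.9 | 55.8 to 56.7 | 55.3 to 57.8 | 54.2 to 57.9 |
| 20%, 0.50 | 49.6 to 49.5 | 49.3 to 49.6 | 50.4 to 51.0 | 48.9 to 49.8 | 48.9 to 50.0 |
| 40%, 0.60 | 58.1 to 58.1 | 57.3 to 58.7 | 57.0 to 58.8 | 54.4 to 58.5 | 53.9 to 58.5 |

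The gain is -0.1 to 1.8 points for h of 1.5-2 and 0.9 to 4.6 points for h = 3.

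**5. Type I error, no treatment effect, r = 30%.** Unstratified 4.6-5.3%; stratified 4.8-5.3%.

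**6. Attenuation.** With r = 30%, true HR 0.5 (log -0.693), h = 3 and p = 30%, the mean one-step log hazard ratio is -0.657 unstratified and -0.687 stratified, that is, hazard ratios of 0.518 and 0.503.

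**The case against.** The strongest reply is that an unstratified log-rank test is an acceptable primary analysis. Chance imbalance is part of the sampling error that its standard error already covers, and step 5 shows the level is kept. That stands. A reader might infer that the missing adjustment biases the Aim 3 comparison; it does not. The pull toward 1 is the ordinary difference between a marginal and a conditional hazard ratio.

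A reader might also infer a large loss. If one-year readmission were 50-60% in a high-risk group and 15-20% in the rest, a 10-point gap would multiply the hazard ratio by 1.13 to 1.21, and stratifying could add 8 to 9 power points in the most extreme setting. Those rates imply a prognostic hazard ratio from ln 0.5/ln 0.8 = 3.1 to ln 0.4/ln 0.85 = 5.6. The documents give no rates, no indication mix and no Aim 3 effect size, so they do not support that reading. Step 3 also shows that the number of events limits power far more than the missing stratification.

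Three further objections stand in part:

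- Section 3.7 calls its account brief and points to a section not in the text reviewed, so strata or covariates stated there cannot be ruled out.
- The section 3.4 diagnoses can coexist in one patient, so a ready-made single indication does not exist.
- With roughly 34-78 events per pair, many small strata would be unwise.

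These shape the fix. They do not remove the point that a baseline factor likely to be prognostic is already collected and is not named in the analysis.

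**Conclusion.** The point holds as a modest improvement in precision and credibility. The unadjusted Aim 3 test remains valid. The size depends on how prognostic indication is: negligible near a prognostic hazard ratio of 1.5, and worth having near 3, where adjustment also protects the estimate against an unlucky allocation. The range rests on the assumed risk mix, control rates and treatment effects, on 111 per arm without dropout, and on the allocation not balancing indication indirectly through age, sex, body mass index or race. The conflict between sections 3.4 and 3.8 also matters here, because it decides how varied the indications are.

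**What to change.** 1. Reconcile sections 3.4 and 3.8 on whether surgical patients are enrolled.
2. Define two or three collapsed, mutually exclusive indication groups, for example heart failure, other non-surgical, and surgical if enrolled. State a hierarchy for patients with more than one diagnosis.
3. Before unblinding, and before readmission is seen by arm at the interim data analysis listed in Table 4, prespecify a log-rank test stratified by these groups and Cox models stratified by or adjusted for them. Fix a rule for merging strata with few events.
4. Keep the unstratified log-rank test and Cox models as a sensitivity analysis.
5. If the separate Statistical Design and Power section already specifies adjustment, bring section 3.7 into line with it.

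The cost is SAP wording and a derivation rule for a variable built from data already collected, with no added patients. The downsides are a small loss of information if strata are sparse, and a hazard ratio that must be read as conditional on indication.
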